1 BACKGROUND

This study will evaluate the safety, pharmacokinetics (PK), pharmacodynamics (PD) and clinical activity of the novel anticancer drug FT-2102 (olutasidenib), administered to patients with relapsed or refractory acute myeloid leukemia (AML) or myelodysplastic syndrome (MDS). FT-2102 is a potent, selective, orally bioavailable, small-molecule inhibitor of mutated isocitrate dehydrogenase 1 (IDH1) being developed by Forma Therapeutics, Inc. and is intended for the treatment of patients harboring IDH1 mutations, in both hematologic and solid tumors.

The presence of mutations at codon 132 in IDH1 imparts a neomorphic activity to the enzyme, resulting in the production of the "oncometabolite" (R)-2-hydroxyglutarate (2-HG), which has pleotropic roles in tumorigenesis. Studies in genetically engineered mouse models and models derived from cancer patient samples support the hypothesis that mutated IDH1 produces 2-HG, the downstream effects of which cause epigenetic changes that consequently block the proper differentiation of progenitor cells and lead to cancer. These data support the therapeutic rationale that inhibition of mutated IDH1 will lower (R)-2-hydroxyglutarate (2-HG) levels and restore normal cellular differentiation.

The promising preclinical data for FT-2102 support its rapid progression into human AML and MDS trials. Additional studies in patients with hematologic malignancies are planned and studies in patients with solid tumors, including central nervous system (CNS) tumors, that harbor an IDH1 mutation, have been initiated.

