3 STUDY ENDPOINTS

Primary Endpoints

Phase 1

• Incidence and severity of adverse events (AEs), clinical laboratory abnormalities and changes in electrocardiogram (ECG) parameters

Phase 2

- All cohorts except Cohort 2: CR rate (best overall response [BOR] of CR/ CRh) as determined by the investigator per disease-specific criteria. Refer to Appendix 7 for AML and Appendix 8 for MDS response criteria
- Cohort 2: Four-month relapse free survival (RFS) rate.

Secondary Endpoints

Phase 1

- PK parameters derived from FT-2102 concentrations
- Antileukemic or antimyelodysplastic activity as determined by CR, CRh, CRi, MLFS, Marrow CR, PR and SD

Phase 2

- Evidence of clinical benefit (CRi, MLFS, Marrow CR, OR, TI, TTR, DOR, EFS, RFS, OS, and other definitions of response, including SD)
- Incidence and severity of adverse events (AEs), clinical laboratory abnormalities and changes in ECG parameters
- PK parameters derived from plasma FT-2102 concentrations

Exploratory Endpoints

Phase 1 and Phase 2

- Changes in 2-HG levels (PD biomarker) in plasma
- Cancer-associated mutations and/or genetic alterations, in bone marrow aspirates and/or peripheral blood
- PK/PD in relationship with clinical safety and clinical activity

Phase 2

• Health-related QOL of patients as assessed by a patient-reported questionnaire

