9.2.6 Pharmacodynamic Analysis

Pharmacodynamic analysis will be performed in patients in the PK Analysis Set.

All PD data will be presented in tabular and/or graphical format and summarized descriptively. Absolute change from baseline and/or percentage change from baseline will be summarized by dose level. Patients in the dose expansion portion of this study will be considered a separate cohort for the purposes of these presentations.

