ECOG Performance Status by visit will be summarized in a shift table for the Safety analysis set. The summary will also include shift to worst post-baseline value. Shifts to nominal time points will not include unscheduled visits; the shift to worst post-baseline value will include unscheduled visits. All ECOG scores will be presented in a data listing.

IX. Pharmacokinetic Analyses

Pharmacokinetic analysis will be performed in patients in the PK analysis set, and data will be listed for all patients in the Safety analysis set. Protocol Section 6.4 provides the PK sample collection time points.

Pharmacokinetic concentration data will be listed by patient including actual sampling times relative to dosing. Plasma concentrations will be summarized by phase, treatment (dose, schedule, single agent or combination therapy), cohort, and nominal visit. The following descriptive statistics will be presented at each nominal time point: n, arithmetic mean, standard deviation, coefficient of variation (CV%), geometric mean, geometric standard deviation, geometric CV%, median, minimum and maximum values.

X. Pharmacodynamic Analyses

Pharmacodynamic analysis will be performed in Phase 1 patients in the PD analysis set, and listed for patients in the Safety analysis set. See Protocol Section 6.5 for the PD assessment time points.

Concentration of 2-HG (including absolute change from baseline and/or percentage change from baseline) will be listed by patient and will be summarized by phase, treatment (dose, schedule, single agent or combination therapy), cohort, and nominal visit. The following descriptive statistics will be presented at each nominal time point: n, arithmetic mean, standard deviation, coefficient of variation (CV%), geometric mean, geometric standard deviation, geometric CV%, median, minimum and maximum values.

Geometric mean 2-HG concentration versus time profiles and/or geometric mean change from baseline versus time for each cohort will be presented graphically on a linear-linear and/or log-linear scale (as appropriate).

XI. Efficacy Analyses

Efficacy endpoints will be listed for all patients in the FAS, unless otherwise specified. Hematologic parameters evaluated for efficacy will be included in the laboratory listings, and listed for the Safety analysis set.

A. Efficacy Endpoints

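### SAP Section X applies geometric statistics to 2-HG changes that are expected to be negative, and leaves the Phase 2 2-HG data listed but not summarised

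*SAP*

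**What the plan says.** **Statistics.** SAP Section X (Pharmacodynamic Analyses) names two forms of change: "Concentration of 2-HG (including absolute change from baseline and/or percentage change from baseline) will be listed by patient and will be summarized by phase". One list of statistics then serves concentration and change alike: "n, arithmetic mean, standard deviation, coefficient of variation (CV%), geometric mean, geometric standard deviation, geometric CV%, median, minimum and maximum values". For figures it says: "Geometric mean 2-HG concentration versus time profiles and/or geometric mean change from baseline versus time for each cohort will be presented graphically", on a linear axis, a log axis or both, as appropriate. No ratio to baseline or log-ratio is named in the section.

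**Direction.** Protocol Section 1 gives the rationale that "inhibition of mutated IDH1 will lower (R)-2-hydroxyglutarate (2-HG) levels and restore normal cellular differentiation".

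**Population.** SAP Section X opens: "Pharmacodynamic analysis will be performed in Phase 1 patients in the PD analysis set", with a listing for the Safety analysis set. It refers to protocol Section 6.5 for the sampling times. Protocol Section 3 places "Changes in 2-HG levels (PD biomarker) in plasma" among the exploratory endpoints for both phases, and SAP Section II.C repeats the matching objective for both.

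**Analysis set.** Protocol Section 9.2.6 says: "Pharmacodynamic analysis will be performed in patients in the PK Analysis Set". Protocol Section 9.2.3 and SAP Section VI.I both define a PD Analysis Set with no phase limit.

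**The concern.** A geometric mean works on logarithms, so it needs positive values. If the drug does what it is given to do, both named forms of change are negative in most patients, and the geometric rows for change and the geometric-mean-change plot cannot be produced as specified. A programmer is not told to substitute a ratio, so the choice of workaround is left open.

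The population sentence is a separate matter. Followed literally, it leaves a stated Phase 2 endpoint without any summary, and it conflicts with the instruction in the same section to summarise by phase and cohort.

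**Working it through.** The documents give no 2-HG values and no figure to reproduce. The first three steps therefore check the definition, using assumed data; the last two compare the texts.

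**1. Definition.** Geometric mean = exp(mean of ln x), geometric SD = exp(SD of ln x), and geometric CV% depends on the same SD of ln x. All three require every x > 0. Absolute change is post − baseline; percentage change is 100 × (post/baseline − 1). Both are below zero whenever 2-HG falls. The ratio post/baseline is positive whenever both concentrations are.

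**2. Invented four-patient example.** Baselines 1000, 2000, 500, 4000; post values 100, 300, 40, 900.
- Absolute changes: −900, −1700, −460, −3100. Geometric mean undefined.
- Percentage changes: −90, −85, −92, −77.5. Geometric mean undefined.
- Ratios: 0.10, 0.15, 0.08, 0.225. Their product is 0.00027 and its fourth root is 0.128. Geometric mean percentage change is 100 × (0.128 − 1) = −87.2%.

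**3. How often this would arise.** Assume a lognormal post/baseline ratio with median m and log-SD s. The share of patients with a fall is Φ(−ln m / s). For example, m = 0.5 and s = 0.9 gives 0.693/0.9 = 0.77 and Φ(0.77) = 0.78.

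| Assumed median fall | s = 0.5 | s = 0.9 |
|---|---|---|
| 50% (m = 0.5) | 92% | 78% |
| 80% (m = 0.2) | 99.9% | 96% |
| 95% (m = 0.05) | nearly 100% | 99.96% |

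Take 20 patients, the number at the MTD/MED in protocol Section 9.2.2.1. Even in the mildest case the chance that all 20 changes are positive is about 0.22^20 ≈ 7 × 10⁻¹⁴. In simulated groups of 20, the geometric mean of absolute and of percentage change was undefined in all six scenarios. The geometric mean ratio was defined in each, at about 0.50, 0.20 and 0.05, which is −50%, −80% and −95%.

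**4. Phase 2.**
- Endpoint and objective: both phases (protocol Section 3, SAP Section II.C).
- Sampling: protocol Table 5 schedules predose samples at C1D1, C2D1, C3D1 and C4D1 in Phase 2, with or without Holter monitoring. Collection stopped at Version 7/Amendment 6.
- PD Analysis Set: no phase limit.
- SAP Section X: analysis in Phase 1 only, yet summaries by phase and cohort.
- SAP Section I: a separate document takes PK, and PK/PD in relation to clinical safety and activity. The 2-HG change summary is not named there.

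The result is that Phase 2 2-HG values appear in the Safety-set listing and in no planned summary.

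**5. Analysis set.** Protocol Section 9.2.6 uses the PK Analysis Set, which needs a calculable PK parameter and excludes certain major deviations. SAP Sections VI.I and X use the PD set.

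**The case against.** The strongest reply is that little is lost. The same list gives n, arithmetic mean, SD, median, minimum and maximum, all valid for either form of change. Geometric mean concentration is valid too, and the figure sentence lets the sponsor plot that alone. The list matches the PK list in SAP Section IX, and geometric mean change on a log axis makes sense if a fold-change was meant. This stands as a limit on the harm. It does not supply the missing definition, because the section names only absolute and percentage change.

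A reader might infer that the 2-HG summary would come out with the wrong sign. Under assumed geometric mean ratios of 0.1, 0.2 and 0.3 (log-SD 0.8, 0.8 and 1.0), keeping only positive changes would give roughly +15%, +20% and +39%. That requires software that silently drops values, which the documents do not describe, as well as invented distributions. Under those same assumptions, the chance that a group of 20 contains even one positive change is 4%, 36% and 91%, so in the first case the cell would almost always be blank.

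A reader might also infer that Phase 2 2-HG is not analysed at all, for up to 429 patients. The documents do not support this. The values are listed, and the separate PK/PD document may use them. Protocol Section 9.2.6 has no phase limit. The RP2D of 150 mg BID was also given in the Phase 1 expansion cohorts (protocol Section 1.5.1), so Phase 1 summaries cover that dose. The 429 is a planned enrolment ceiling: sampling ended at Amendment 6, and patients may re-enrol across cohorts. None of this gives a reason for omitting a Phase 2 summary.

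On the analysis set, the SAP states that it governs the analysis, so the practical choice is already made and only the protocol text lags.

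**Conclusion.** The point holds, at minor severity. As written, the geometric statistics for absolute and percentage change in 2-HG, and the optional plot of geometric mean change, are undefined for the decreases expected. That follows from the definition and the stated direction of effect; the shares of 78% to nearly 100% rest on the assumed lognormal ratios. It would be wrong to say that the on-target summary as a whole fails, because the arithmetic, median and concentration summaries survive.

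The Phase 1 restriction contradicts both the endpoint's scope and the section's own by-phase instruction, so the Phase 2 data are listed but not summarised. The number of Phase 2 patients affected cannot be stated, because the documents do not say how many samples were taken or assayed before Amendment 6. The endpoint is exploratory and untested, dose escalation is complete, and no dose or efficacy conclusion rests on these rows.

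**What to change.** In SAP Section X:
- Restrict geometric mean, geometric SD and geometric CV% to 2-HG concentration and the post/baseline ratio.
- Report percentage change as 100 × (geometric mean ratio − 1), and plot the ratio on the log axis.
- Keep arithmetic mean and median for absolute and percentage change.
- Extend the population sentence to Phase 1 and Phase 2 patients in the PD analysis set, summarised by cohort, using samples collected before Amendment 6. Do not pool cohorts: Cohort 2 enters in remission, and some Cohort 6 patients continue FT-2102 up to re-enrolment, so their baselines differ in kind.

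In protocol Section 9.2.6, replace the PK Analysis Set with the PD Analysis Set that the SAP already uses.

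The cost is SAP and protocol wording and a few extra table columns, with no new sampling. It assumes that the Phase 2 samples taken were assayed.

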Time to response (TTR): TTR is the time in months between the first dose of study drug and documentation of the first overall response for patients who achieve a PR or better. This analysis will be performed only on patients who have achieved PR or better as a best overall response. Kaplan Meier analyses will not be performed; summary will be descriptive. This analysis will not be performed on Phase 2 Cohort 2, as it is not applicable since patients enter the study already in response.

Duration of CR/CRh (DCR/CRh): DCR/CRh is the time in months between documentation of the first CR or CRh until the date of relapse or death, whichever is earlier. Patients will be censored as per Table 1. DCR/CRh will only be calculated for patients who achieve a CR or CRh as the best response.

Duration of complete remission (DCR): DCR is the time in months between documentation of the first CR until the date of relapse or death, whichever is earlier. Patients will be censored as per Table 1. DCR will only be calculated for patients who achieve a CR as the best response.

Duration of overall response (DOR): Duration of overall response will be calculated similarly to DCR but will assess the time in months between documentation of the first response of PR or better until the date of relapse, death, whichever is earlier. Patients will be

censored as per Table 1. This analysis will not be performed on Phase 2 Cohort 2, as it is not applicable since patients enter the study already in response.

Patients who respond and stop FT-2102 to undergo HSCT will continue to be followed until relapse. Duration of response endpoints (DRC/CRh, DCR, DOR) for these patients will encompass time between HSCT and relapse ordeath. For patients with no report of relapse by the end of the follow-up data collection, duration of response (DCR/CRh, DCR, DOR) will be censored as per Table 1.

A separate sensitivity analysis will be conducted for duration of response of Phase 2, Cohort 1 patients, which analyzes duration of response as described above, but for those patients who have enrolled under Phase 2 Cohort 2 due to MRD positivity, the duration of response will be the total duration of response experienced in Cohort 1 and Cohort 2 together.

An additional sensitivity analysis will be performed on DCR/CRh, DCR, and DOR in which HSCT will be handled as the end of response.

Since this study was ongoing during the COVID-19 pandemic, a sensitivity analysis will be performed on OS, DCR, DCR/CRh, and DOR in which patients who have died due to COVID-19 will be censored to assess the effect that COVID-19 had on time to event endpoints.

4-Month Relapse-Free Survival (RFS) Rate: The primary endpoint for Phase 2 Cohort 2 AML patients is the 4-Month RFS rate. This will be evaluated by a Simon 2-Stage design described in Section IV.C, testing the null hypothesis that the 4-month RFS rate is < 80%. It is defined as the proportion of patients in Phase 2 Cohort 2 who have not relapsed or died on or before their 4-month response evaluation. If a patient does not receive a disease response assessment at their 4-month visit but has a subsequent disease response assessment on or after study day 120 that shows non-progression/ non-relapse, they will be evaluated as having achieved 4-month RFS. This rate is not calculated for MDS patients, or for AML patients in any other cohort.

Relapse-Free Survival (RFS): RFS will be calculated for all patients in Phase 2 Cohort 2, who are patients who have achieved a response of CRi or better. It is the time in months between the date of first dose until relapse, start of other (non-protocol study drug) new antileukemia therapy, or death from any cause, whichever occurs first. Hematopoietic stem cell transplant (HSCT) is not considered an event for RFS. For a patient who is responding and experiences none of these events before the end of study follow up, RFS will be censored as per Table 1. The percentage of patients with RFS will be estimated at landmark timepoints.

Event-free survival (EFS): EFS is defined as the time in months between first dose of study drug and disease progression, relapse, death from any cause, treatment failure, or start of other (non-protocol study drug) new antileukemia therapy, whichever occurs first. HSCT is not an event for EFS, and patients experiencing HSCT will continue to be followed until an event occurs. For EFS, treatment failure will be operationally defined as not achieving a best

overall response of CR, CRh, or CRi on study. The date of treatment failure for patients with this event will be the date of the last response assessment while on study.

For a patient with none of these events before the end of study follow-up, EFS will be censored as per Table 1. For patients lost to follow-up prior to any evidence of event, the EFS data will be censored at their last completed assessment date that is SD or better prior to the initiation of anti-cancer therapy.

Overall survival (OS): OS is defined as the time in months from the first dose of study drug until death from any cause. For patients who are not known to have died by the end of study follow-up, OS will be censored on the date the patient was last known to be alive.

Transfusion independence (TI): Patients will be classified as "dependent" or "independent" at baseline within each category of platelets, pRBC, any (i.e., receiving either platelets or pRBC or both) and both (i.e., receiving both platelets and pRBC) if they received a transfusion within 8 weeks prior to the first dose of FT-2102. TI will be defined as patients who experience at least a 28-day or 56-day period during any point on treatment with no transfusion of that type required. For the "both" category, patients who are classified as dependent must have received both a platelet and pRBC transfusion within the 8 weeks prior to baseline, and to be classified post baseline as independent, they must experience a 28 or 56 day minimum duration on study where they did not require a transfusion of either platelets or pRBC.

B. Efficacy Analysis

Any response assessment occurring after the start of alternate anti-cancer therapy will not be included in the analyses using response assessments.

Note that some patients who were assigned to single agent therapy in Phase 1 requested to start combination therapy with azacitidine when a response was not observed on single agent treatment. In such cases, upon beginning dosing with azacitidine (if the patient was assigned to single agent therapy), then response assessments occurring after the first dose of azacitidine will not be included in efficacy analyses. Time to event analyses for such instances will be treated as if the patient has experienced disease progression when azacitidine is initiated.

The overall survival and event-free survival analyses will be based on patients in the FAS. All other efficacy analyses will be based on patients in the EE analysis set as the primary analysis, with selected analyses on the FAS and PP analysis set as supportive. The following table indicates the analysis sets to be analyzed for each endpoint.

		A	alysis S	et
Endpoint	Patients Analyzed	EE*	FAS	PP*
CR/CRh Rate,				
DCR/CRh, TTCR/CRh	AML only	Х	Х	Х
CRR, DCR, TTCR	Each disease group separately	х	Х	Х
ORR, DOR, TTR	Each disease group separately	х	Х	х
Best overall Response	Each disease group separately	х	Х	Х
4-month RFS Rate	Phase 2 Cohort 2 only		Х	
RFS	Phase 2 Cohort 2 only		Х	
EFS, OS	All patients combined		Х	
TI	All patients combined	х	х	

*EE and PP analyses will only be performed for IA2.

CR/CRh rate will be analyzed for all cohorts except Phase 2 Cohort 2. For Phase 2 Cohort 1, to test the hypothesis that the CR/CRh rate is greater than 15%, a 1-sided exact test for a binomial proportion will be performed. If the exact one-sided p-value is less than 0.0245, the alternative hypothesis will be accepted. This is equivalent to at least 36 CR/CRh responses of 173 EE patients.

For Phase 2, Cohorts 3, 4, and 5 test the hypothesis that the 85% confidence interval for the CR/CRh rate does not include 10%. If there are 5 or more CR/CRh responses of the 20 patients in these cohorts, the 85% confidence interval will be greater than 10%, and the alternative hypothesis that the response rate is greater than 10% will be accepted.

Phase 2 Cohorts 6, 7, and 8 are Simon 2-Stage designs and the primary efficacy endpoint will be evaluated via the number of CR/CRh responses stipulated in the design criteria described in Section IV.C.

The number and proportion of patients achieving CR/CRh response will be reported by cohort from the binomial proportion, along with Clopper-Pearson 95% confidence interval for AML and MDS patients respectively. Appendix 2 provides the SAS code.

For Phase 2 Cohort 1, a sensitivity analysis will be performed on the CR/CRh rate in which Atkinson and Brown confidence intervals will be calculated.

4-Month RFS, BOR, ORR, TI: The proportional endpoints listed here will be summarized as the number and percentage of patients within each category, and will be presented by cohort along with Clopper-Pearson 95% confidence intervals. The 4-month RFS endpoint will be analyzed for Phase 2 Cohort 2 only.

RFS, EFS, OS, TTCR/CRh, TTCR, TTR, DCR/CRh, DCR, DOR: Time to event endpoints listed here will be expressed as the number of months from first dose to the event and will be analyzed using Kaplan-Meier (KM) methods for each cohort, with the exception of TTCR/CRh, TTCR, and TTR, since these analyses are performed only on the subset of responders and censoring is unnecessary. The analysis will include median, 1st and 3rd quartiles for time calculated using Kaplan-Meier methods, and the 95% confidence interval for the median

calculated using the Brookmeyer-Crowley method. The estimated probability of survival over time for RFS, EFS, OS, DCR/CRh, DCR, and DOR will be plotted as KM curves for Phase 2 Cohort 1, with the exception of RFS, which will be performed for Phase 2 Cohort 2 only. Appendix 2 provides the SAS code.

The survival probability and 95% confidence interval will be estimated at selected landmark timepoints of: 3 months, 6 months, 12 months, and 24 months based on Kaplan-Meier product-limit method and Greenwood's formula. A month will be calculated as time in days divided by 30.4375.

Table 1. Censoring Rules

Case	Censoring Rule
Patient has no post baseline assessments	Censor at date of first dose
and no date of death recorded	
Patient did not die or experience PD or	Censor at date of last adequate response
relapse*	assessment (any response assessment that is
	not "Not Evaluable" or "Not Done")
Patient in Phase 1 started on single agent	Censor at date of last adequate response
therapy, but switched to combination	assessment prior to the combination therapy
therapy	

*For patients who discontinue FT-2102 treatment to receive HSCT and remain on study to be followed until documented disease relapse, confirmation of relapse is not required in this situation, and a single occurrence of relapse will be considered as documented "confirmed" relapse in analyses of response.

The following sensitivity analyses of DCR/CRh will be performed with censoring rule variations in EE patients:

- 1. Patients who undergo HSCT will be censored at the last adequate assessment prior to HSCT
- 2. Patients who discontinued study treatment due to undocumented progression will be considered as events at the date of last dose
- 3. Patients with subsequent anti-cancer therapies prior to an event date will be considered to be censored the day before the start of the anti-cancer therapy.
- 4. Patients with subsequent anti-cancer therapies prior to an event date will be considered as having an event as the start of the anti-cancer therapy.
- 5. Patients who didn't have an event and are still on treatment will be censored at the last treatment date, otherwise will be censored at the last response assessment.

For DOR and DCR HSCT sensitivity analysis will be performed, where patients who undergo HSCT will be censored at the last adequate assessment prior to HSCT. The following subgroup analyses will be performed:

• CR/CRh rate, ORR, DCR/CRh – For AML patients in the EE analysis set: AML type (primary or secondary), disease state (relapsed/refractory or treatment naive), AML cytogenetic risk classification, IDH1 mutation type, IDH1 mutation confirmed by

central lab, age group, sex, region, race, baseline ECOG PS, prior HSCT for AML, prior HMA, prior IDH1 therapy, and prior FT-2102 therapy.

• OS, EFS – For AML patients in the FAS analysis set: AML type (primary or secondary), disease state (relapsed/refractory or treatment naive), AML cytogenetic risk classification, IDH1 mutation type, IDH1 mutation confirmed by central lab, age group, sex, region, race, baseline ECOG PS, prior HSCT for AML, prior HMA, prior IDH1 therapy, and prior FT-2102 therapy.

Kaplan Meier plots will not be produced for subgroup analyses.

Transfusion Independence

Transfusion independence will be analyzed as part of the clinical benefit expected from FT-2102. The percentage of patients who are transfusion dependent at baseline will be summarized (overall and by type of blood product of RBC and/or platelets). The proportion of patients who became transfusion independent during any 28-day and 56-day period during treatment will be summarized by best overall response on study. Percentages will be based on the number of patients within the best overall response category.

Swim Lane Plot of Time on Treatment and Duration of Response

A swim lane plot will be created for patients in the FAS population to visualize the time on treatment with FT-2102. Time of first response and time of HSCT will be annotated on the plot. The length of the bar will represent the time (in weeks) on study, including both time on active treatment of FT-2102 and time in follow-up. The bar will be one color during active treatment, and then patients who stop treatment but are still being followed for continuing response will have the bar turn a different color. Patients who are still ongoing (either on treatment with or without response, or off treatment but being actively followed for response) will be indicated with arrows at the end of the bar. Best overall response will be annotated at the end of the bar.

A repeat of the swim lane plot will be done where there is no color coding by on/off treatment status. Rather, the bar will change color if/ when 28 days of transfusion independence is achieved. The length of the bar will represent the time (in weeks) on treatment. Best overall response will be annotated at the end of the bar.

Forest Plot

At IA2, A forest plot will be created for Phase 2 cohort 1 patients in the EE analysis set to present the CR/CRh rate compared across all of the relevant subgroups specified in the section VI.J; the subgroups not applicable to this cohort and excluded from the forest plot are diagnosis, disease state, prior IDH-1 therapy, prior FT-2102 treatment, and renal function. The plot will show the point estimate of each rate with 95% CI.

A similar plot will be created to present ORR for Phase 2 cohort 1 patients in the EE analysis set.

Hematologic Efficacy Analyses

Hematologic efficacy analyses will be performed for IA2 only.

The absolute and percent change in marrow blasts from baseline will be tabulated by visit and maximum post baseline decrease. This table summarizes blasts from either the bone marrow biopsy or bone marrow aspirate form together. At each nominal visit, if there is both a bone marrow biopsy result and a bone marrow aspirate result reported, the aspirate result will be used. Blast results of "less than 5%" will be imputed as 4.9%. No summaries will be presented when fewer than five patients' data are available at an assessment time point.

A waterfall plot will be created for Phase 2 cohort 1 patients in the EE analysis set to present the maximum % decrease in blast % experienced on study.

Line plots showing the mean (+/- SE) bone marrow blasts, ANC count, hematocrit, platelet count will be presented over time on Day 1 for cycles 1-15 for patients in the Phase 2 Cohort 1 FAS and EE analysis set by best response (CR/CRh, non-CR/CRh responders, and non-responders).

Efficacy Profiles

For IA2, For those patients who have a best overall response of PR or better, patient plots of ANC, platelet count, hemoglobin, and bone marrow blasts (analyzed as described above) will be produced for all patients in the Phase 2 Cohort 1 FAS and for patients in the Phase 1 FAS whose starting dose of FT-2102 was 150 mg BID.

C. Quality of Life Analysis

The EQ-5D-5L consists of five dimensions: mobility, self-care, usual activities, pain/ discomfort, and anxiety/depression. Each dimension has 5 levels of health state: no problems, slight problems, moderate problems, severe problems and extreme problems. The patient indicates his/her health state by selecting the most appropriate statement in each of the five dimensions. This decision results in a 1-digit number that expresses the level selected for that dimension. The digits for the five dimensions can be combined into a 5-digit number that describes the patient's health state. Present overall state of health is also to be rated on a vertical visual analogue scale (VAS) from 0 (worst health) to 100 (best health). This assessment was only performed on Phase 2 patients. EQ-5D-5L data will be summarized from the screening visit through cycle 8 for the FAS (Phase 2) and EE analysis sets (Phase 2).

Five domains of EQ-5D-5L

The number and percentage of patients reporting each score per dimension will be summarized, as well as the number reporting some problems on that dimension (score >1). Also, the change from baseline in the number reporting some problems in each dimension will be reported (raw and percent change). An additional summary table will be produced that summarizes the EQ-5D-5L data by best response (3 groups: CR/ CRh, Other Responders, Non-Responders). Missing data will be imputed as described in Section VI.C.

A stacked bar chart will be produced to illustrate the domain values. In the chart, the x axis will represent nominal visit (screening, cycle 2, cycle 3, etc.) and the y axis will represent percentage. Each bar will add to 100% and be color coded to represent the percent of patients reporting each level (1-5) of problems within the dimension for that visit. A separate chart will be created for each of the dimensions. This figure will only be created for the

Phase 2, Cohort 1, EE analysis set. The figure will also be produced by best overall response, as described above for the summary table.

VAS score of EQ-5D-5L

The VAS score of overall state of health will be summarized by descriptive statistics (mean, standard deviation, median, Q1, Q3, minimum, maximum) by visit, as well as the number and percentage of patients reporting bad overall state of health (score < 80). An additional summary table will be produced to summarize change from baseline to first response for CR/CRh and Other Responders, or change from baseline to best score for non-responders, by descriptive statistics by best response (3 groups: CR/CRh, Other Responders, Non-Responders). Missing data will be imputed as described in Section VI.C.

All EQ-5D-5L data will be listed. In the listing, imputed data will be flagged.

XII. References

Atkinson EN and Brown BW. Confidence limits for probability of response in multistage phase II clinical trials. Biometrics 1985; 41 (3): 741-744.

